Such strategies have been applied effectively in many domains (e.g., organ donation; Johnson & Goldstein, 2003) but have seldom been used to promote health during grocery shopping, which is the leading source of sugar-sweetened beverages and nutrient-poor foods (An & Maurer, 2016). One recent study randomized undergraduates to grocery shop online, receiving either: 1) nutrition education, 2) a financial incentive for selecting healthy foods, or 3) a default shopping cart with healthy foods, which they could alter as desired. The default group chose healthier foods than education controls, with no effect of incentives. This study supports the promise of defaults to encourage healthier purchases when grocery shopping and highlights a need for ecologically-valid studies in populations with diet-related diseases. The present study will fill this gap by testing online grocery shopping and defaults as potential mechanisms

to promote adherence to a diabetic diet among adults with diabetes or at risk of developing diabetes.

These strategies have translational significance as they could be incorporated into clinical treatment: e.g., by “prescribing” online grocery shopping if the Online intervention is efficacious, and/or working with dietitians to generate default carts catering to different lifestyles and disseminating this information in clinical settings and/or via partnerships with grocery stores. As such, the proposed interventions have the potential to improve dietary intake, glucose regulation, weight, and medication needs among diabetic patients. The study team has the substantive expertise needed to examine this question, including a history of behavioral economics, diabetes, grocery shopping/retail, and community-based research (e.g., Anzman-Frasca et al., 2018; Epstein & Saelens, 2000; [name] et al., 2018).

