## 5.0 Study Design\*

5.1 Describe and explain the study design (e.g. case-control, cross-sectional, ethnographic, experimental, interventional, longitudinal, observational).

Response:

This study has an experimental design. Participants will be randomly assigned to 1 of 2 interventions or a control group in which they will shop in-person as usual. Stratification factors will be sex and diabetes status: type 2 diabetic vs. at risk for type 2 diabetes, defined as a diagnosis of prediabetes or meeting criteria for increased risk of developing type 2 diabetes as determined by the American Diabetes Association Type 2 Diabetes Risk Test. In all groups, recipe cards that follow the evidence-based DASH diet and correspond to dietary recommendations for diabetic patients will be provided. The *Online* intervention will utilize online grocery shopping (shopping at a local grocery store via Instacart) to promote healthier purchasing, removing visceral factors that can lead to impulse purchases in stores. The *Defaults* intervention will augment this intervention, showing participants a default cart when they log into their accounts. They will be told that their cart has been filled with items that conform to a diet appropriate for diabetes prevention, management, and overall health and can be used to make the recipes from the provided recipe cards, and that they may modify it as they like.

At baseline, all participants will complete a survey online or via phone and then will grocery shop in-person as usual. Participants will then be randomized and receive further instructions. For the next 3 weeks, they will receive recipe cards and shop in accordance with their assigned study group. The following week (post), they will shop using the method of their choice (in-person, online) and complete a survey again. Household receipt data will be collected throughout the study. The baseline period will also serve as a run-in period, and participants who do not comply with study guidelines for baseline procedures (including guidelines for receipt submission) will not be randomized for further participation. Primary analyses will examine intervention effects on grocery purchases, with additional analyses on spending and dietary intake. All participant interactions will occur online or via phone.

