## **19.0 Data Management and Analysis\***

*19.1 Describe the data analysis plan, including any statistical procedures. This section applies to both quantitative and qualitative analysis.*

Response:

Linear mixed models will be used to test effects of the interventions on total calories, carbohydrates, sugar (total sugar and/or added sugar), and nutritional quality of grocery purchases, with study group, time, and their interaction as factors. Primary comparisons will be between-groups comparisons of these variables at post-test. We will also examine whether these variables differ overall by study group and whether changes in these variables differ by study group. We will conduct each analysis once for the total cart and then again examining these variables relative to household size and for items that the respondent indicated they would be consuming. We will conduct parallel analyses with total dollars spent each week and with DASH diet scores as outcomes to examine effects on spending and intake. We will also explore whether effects differ for participants with prediabetes vs. diabetes and whether results change when adjusting for food purchases beyond the target stores. Finally, we will test for relationships between purchases (calories, carbohydrates, and sugar (total sugar and/or added sugar)) and intake (DASH diet scores). We will also explore whether results differ when considering shopping trips completed by the participant only (vs. all trips for the household).

*19.2 If applicable, provide a power analysis.*

*NOTE: This may not apply to certain types of studies, including chart/records reviews, survey studies, or observational studies. This question is asked to elicit whether the investigator has an adequate sample size to achieve the study objectives and justify a conclusion.*

Response:

To estimate the sample size needed for this study, effect sizes from the most similar existing study were used: a proof-of-principle study examining the effects of defaults, incentives, and education strategies on healthfulness of grocery purchases among undergraduate students (Coffino & Hormes, 2018, Obesity). Based on the observed differences in calories purchased at post-test between defaults and education control groups (Cohen's  $d=0.96$ ), 15 participants would be needed for the primary comparison in the present study, with  $\alpha=.05$  and  $\text{power}=.80$ . We repeated this analysis using the difference between controls and

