the prior study's intermediary group (incentives; Cohen's  $d=0.44$ ) to conduct a more conservative sample size calculation, given our interest in detecting effects on purchasing between our intermediary group (*Online*) and the other groups. This calculation yielded a sample size of 54. We increased this to account for participants lost during the run-in period (i.e. failure to confirm diabetes diagnosis, failure to complete baseline procedures) as well as participants lost due to attrition, with a plan to enroll up to 100 participants.

*19.3 Describe any procedures that will be used for quality control of collected data.*

Response:

Some data will be entered directly by participants (online questionnaires). All other study data will be entered by trained staff: study staff will enter participant responses into online forms while phone screening/phone interviews are completed. Study staff will also enter information from receipts into NutritionistPro (e.g., nutrition information) and Microsoft Excel (e.g., dollars spent) for analysis of study aims. Entered data will be double entered and/or checked for quality control.

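### The effect sizes in Section 19.2 appear to come from a study with every arm shopping online, so the 80% power implied for the Online contrasts is unsupported

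*Combined protocol and SAP*

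**What the plan says.** Section 19.2 bases the sample size on "a proof-of-principle study examining the effects of defaults, incentives, and education strategies on healthfulness of grocery purchases among undergraduate students". It makes two calculations.

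- **d=0.96.** "Based on the observed differences in calories purchased at post-test between defaults and education control groups", the section concludes that "15 participants would be needed for the primary comparison in the present study", at alpha .05 and power .80. The two arms of that comparison are not named.
- **d=0.44.** The calculation is repeated with the earlier study's incentive arm against its controls, "given our interest in detecting effects on purchasing between our intermediary group" (Online) and the other groups, meaning both Control and Defaults. This gives 54, which is raised to a plan to enrol up to 100.

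Section 4.1 describes a study with the same population and the same three strategies: "One recent study randomized undergraduates to grocery shop online, receiving either: 1) nutrition education, 2) a financial incentive for selecting healthy foods", or a default cart. It reports: "The default group chose healthier foods than education controls, with no effect of incentives".

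In this trial, Section 5.1 states: "Participants will be randomly assigned to 1 of 2 interventions or a control group in which they will shop in-person as usual". Defaults is Online plus a pre-filled cart (Section 6.0), and all groups receive recipe cards. Section 19.1 makes the between-group comparisons at post-test primary. Section 12.1 says that in the post-test week participants choose how to shop and are given neither default carts nor recipe cards.

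**The concern.** The Online arm changes one thing relative to Control: shopping moves from the store to Instacart. An effect size for that contrast has to come from a comparison of online with in-person shopping. The study in Section 4.1 had no in-person arm. Its incentive arm shares only a label with Online, that of the intermediate group.

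Aim 1 and hypothesis 1c (Section 2.2) depend on the Online contrasts, and Section 4.1 foresees recommending online shopping to patients if Online works. If a stated 80% power rests on a different treatment compared with a different control, a non-significant Online result could be given more weight than the design supports.

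**Working it through.** **1. Line up the contrasts.**

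| Source contrast | What differs in the source | Use in Section 19.2 | Match in this trial |
|---|---|---|---|
| Defaults vs education, d=0.96 | Default cart vs education, both online | Primary comparison, arms not named | No direct match: at post-test there is no cart and shopping mode is free |
| Incentives vs education, d=0.44 | Financial incentive vs education, both online | Online vs Control and Online vs Defaults | None: no arm has an incentive, and the source has no in-person arm |

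The documents give no effect size for online versus in-person shopping.

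**2. Reproduce 15 and 54.** Section 19.2 does not state the test. A search over common settings reproduces both figures only as totals over three arms:

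- Group-by-time interaction, f=d/2, 3 groups, 2 measurements, correlation 0.5: N=14, rounded up to 15, and N=53, rounded up to 54.
- The same test with 4 measurements and correlation 0.3: 13 to 15, and 52 to 54.
- One-way three-group ANOVA with f set equal to d: 13.9 to 15, and 52.9 to 54.

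A two-arm comparison of means does not reproduce the pair. Using n per arm = 2 × ((1.96 + 0.842)/d)²:

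- d=0.96: 2 × 7.85/0.9216 = 17.03, so 18 per arm (19 by the t-test).
- d=0.44: 2 × 7.85/0.1936 = 81.1, so 82 per arm (83 by the t-test), or 3 × 83 = 249 over three arms.

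The figure 54 cannot be per arm, since 3 × 54 = 162 exceeds the enrolment limit of 100.

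**3. Power for the pairwise post-test comparison.** Two-sample t-test, two-sided alpha .05, equal allocation (sidedness and allocation ratio are not stated, so both are assumptions). Noncentrality = d × √(n/2), df = 2n − 2.

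| n per arm | Basis | √(n/2) | Noncentrality at d=0.44 | Power at d=0.44 | Detectable d at 80% power |
|---|---|---|---|---|---|
| 18 | 54/3 | 3.00 | 1.32 | 25% | 0.96 |
| 33 | 100/3, no loss | 4.06 | 1.79 | 42% | 0.70 |

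If 54 is read instead as two arms of 27, power at d=0.44 is 36%.

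**4. Two separate problems.** Step 1 shows that d=0.44 is not an estimate for the Online contrasts, however 54 was computed. Step 3 shows that, even if d=0.44 is accepted, 80% power does not hold for a pairwise post-test comparison. The second problem comes from the test behind 54 and would remain with a well-matched effect size.

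**The case against.** The protocol is open that it uses the most similar study available. It calls itself a pilot (Section 8.4) and aims to inform larger work (Section 12.1). No better effect size can be drawn from the documents, and nothing in Section 19.1 says that a null result will be read as no effect. All of this stands and limits the remedy to wording.

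Section 4.1 gives no citation for the study it describes. That it is the study cited in Section 19.2 is inferred from the same population and strategies. The inference is strong, but it remains an inference.

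It could also be said that the mixed model gains precision from baseline. Section 19.1 does not state a baseline adjustment. If one were used, n = 2(1 − ρ²) × ((1.96 + 0.842)/0.44)² gives 61 per arm at ρ=0.5 and 42 at ρ=0.7. Both exceed 33.

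A reader might infer more than the documents support:

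- **That d=0.96 belongs to Defaults vs Online.** As Section 4.1 describes the source, the cart was part of the shopping being compared. Here the primary comparison is made after the cart is withdrawn, and the source controls had education where every arm here has had recipe cards. Reassigning 0.96 would create a new unsupported power claim.
- **That the plan implies d = 0.96 − 0.44 for Defaults vs Online.** The plan never subtracts. It uses 0.44 for Online against both other groups.
- **That the reported lack of an incentive effect means d=0 for Online.** That sentence concerns healthier choices, whereas the d=0.96 is for calories and the second calculation repeats that analysis. A non-significant result is compatible with d=0.44, and an incentive effect cannot anchor an online effect in either direction.
- **That calling the second calculation more conservative is wrong.** The phrase describes a smaller d giving a larger sample, which is accurate.

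**Conclusion.** The concern holds in a limited form. Neither source effect is a matched estimate for a post-test contrast in this trial, and the implied 80% power for Online vs Control and Online vs Defaults is unsupported. The figure that matters is d=0.44, because it led to 54 and then 100; the 15 from d=0.96 was superseded. At the planned size the pairwise post-test comparison can detect about d=0.96 (18 per arm) to d=0.70 (33 per arm) with 80% power. The upper size is a best case, since losses in the run-in and afterwards are expected.

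This rests on the Section 4.1 study being the cited source, a two-sided 5% level, equal allocation and an unadjusted comparison of two means. It does not show that the trial is too small for its purpose as a pilot, nor what the true effect of online shopping is.

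**What to change.** In Section 19.2:

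1. State that both source effects were observed with all groups shopping online (after confirming this against the cited paper), and that they are assumptions, not matched estimates, for this trial's contrasts.
2. Name the pairwise post-test contrasts: Defaults vs Control, Online vs Control and Defaults vs Online.
3. State the test and settings that gave 15 and 54.
4. Replace the 80% power claim for the Online contrasts with the minimum detectable difference at the planned size: about d=0.96 at 18 per arm and 0.70 at 33 per arm.

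In Section 19.1, add that the Online contrasts will be reported with confidence intervals. Do not present d=0.96 as the sized effect for Defaults vs Online.

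The cost is a change of wording in two sections, with no extra participants or data. The downside is a less favourable stated figure for the Online contrasts.

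### The sample sizes of 15 and 54 in section 19.2 do not follow from the stated pairwise effects; 54 in three equal arms gives about 25% power for d=0.44, not 80%

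*Combined protocol and SAP*

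**What the plan says.** Section 5.1 sets up three groups: "Participants will be randomly assigned to 1 of 2 interventions or a control group". Section 19.1 fits linear mixed models with group, time and their interaction, and names the main contrasts: "Primary comparisons will be between-groups comparisons of these variables at post-test".

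Section 19.2 takes its effect sizes from an earlier grocery-purchasing study in undergraduates. For the difference between the defaults and education control groups (Cohen's d of 0.96 in calories, alpha .05, power .80) it says that "15 participants would be needed for the primary comparison in the present study". It then repeats the calculation with the incentives-versus-control difference (d of 0.44), "given our interest in detecting effects on purchasing between our intermediary group" (Online) and the other two groups. The result: "This calculation yielded a sample size of 54". That figure is raised for run-in losses and attrition, "with a plan to enroll up to 100 participants". No loss rate is given.

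The section does not name the test, its sidedness, the allocation ratio or any effect-size conversion. It does not say whether 15 and 54 are totals or per-group numbers.

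**The concern.** Cohen's d describes a gap between two groups. The stated reason for using 0.44 is also a gap between two groups: Online against each of the others. A d of 0.44 is a moderate effect, and 54 people across three arms leaves 18 per arm, which is few for detecting it.

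Hypothesis 1c places Online between Defaults and Control, and hypothesis 1a compares Defaults with the other groups, Online included. If the stated 80% does not apply to these contrasts, a non-significant Online result could be given more weight as evidence of no effect than the design allows. Section 4.1 raises the possibility of recommending online shopping clinically if it works, so that result matters.

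**Working it through.** **Inputs.** From section 19.2: d=0.96, d=0.44, alpha .05, power .80, stated sizes 15 and 54, ceiling 100. From section 5.1: three groups. Assumed because not stated: two-sided test, equal allocation, no multiplicity adjustment, and 15 and 54 as totals (the per-group reading is checked in step 4).

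**1. Reproducing 15 and 54.** In a one-way analysis of variance with three groups, the noncentrality is N × f², with 2 and N − 3 degrees of freedom. Setting f equal to d:
- f=0.96: 15 × 0.96² = 13.82, power .84. The next smaller balanced total, 12, gives .71.
- f=0.44: 54 × 0.44² = 10.45, power .81. A total of 51 gives .78.

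These are the protocol's two figures. A second route gives the same pair. For a group-by-time F test with m time points and correlation rho, the noncentrality is N × f² × m/(1 − rho). With f=d/2, m=2 and rho=0.5 this is N × (d²/4) × 2/0.5 = N × d², again with 2 and N − 3 degrees of freedom.

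The first route mis-scales the effect. For three groups whose largest gap is d, f lies between d × √(1/6) = 0.41d and d × √2/3 = 0.47d. For d=0.44 that is 0.18 to 0.21. With 54 participants the omnibus test then has 19% to 24% power, and 80% would need 303 to 228 in total.

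**2. Size for the pairwise contrast.** The normal approximation is n per group = 2 × (1.96 + 0.84)²/d², about 15.7/d². This gives 17.0 (rounded up, 18) for d=0.96 and 81.1 (82) for d=0.44. The exact noncentral t adds one to each:
- d=0.96: 19 per group (18 gives 79.9%), so 3 × 19 = 57.
- d=0.44: 83 per group, so 3 × 83 = 249.

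**3. Power at the planned sizes.** Noncentral t with noncentrality d × √(n/2) and 2n − 2 degrees of freedom:

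| Total (per arm) | d | Noncentrality | Power |
|---|---|---|---|
| 15 (5) | 0.96 | 1.52 | 27% |
| 54 (18) | 0.96 | 2.88 | 80% |
| 54 (18) | 0.44 | 1.32 | 25% |
| 100, no losses (33) | 0.44 | 1.79 | 42% |

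The difference detectable with 80% power is about d=0.96 at 18 per arm and 0.70 at 33 per arm.

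**4. More favourable readings, for d=0.44.**
- One-sided: the sizes become 15 and 65 per group. The first matches the protocol and the second does not. Power at 18 per arm is 36%.
- 54 per group: 62% two-sided, 73% one-sided. It would also need 3 × 54 = 162 participants, above the ceiling of 100.
- Change from baseline at rho=0.5: the standard deviation of change is SD × √(2 × (1 − 0.5)) = SD, so power stays at about 25%.
- Baseline adjustment at an assumed correlation r, replacing d by d/√(1 − r²):

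| r | Adjusted d | 18 per arm | 33 per arm |
|---|---|---|---|
| 0.5 | 0.51 | 32% | 53% |
| 0.7 | 0.62 | 44% | 69% |
| 0.8 | 0.73 | 57% | 83% |

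Only the last cell reaches 80%. It needs all 100 enrolled to be randomised and retained, and a correlation that the protocol does not state.

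**The case against.** The best defence is that the plan does not clearly commit to pairwise tests. Section 3.0 speaks of group differences across three arms, section 19.1 includes the group-by-time interaction, and hypothesis 1b concerns change. An omnibus or interaction test is therefore not foreign to the plan, and one such test gives 15 and 54. This stands as a reason not to say how the figures arose. A reader might infer that d was certainly entered as f by mistake. The match makes that a likely explanation if the calculation was for the post-test comparison, but the interaction route fits equally well and the documents do not settle it. Neither route supplies the power claimed for Online against another group, which is the stated reason for the second calculation.

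It is also fair that the contrast section 19.2 treats as primary, Defaults against Control at d=0.96, has about 80% power at 18 per arm, and that planning used 54, not 15. Sections 8.4 and 12.1 present the study as a pilot for larger work.

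Two further inferences should be resisted. One is that the Online contrasts will be null whatever the truth. At 18 per arm power is 53% for d=0.70 and 80% for d=0.96, so the shortfall is specific to true effects near 0.44. The other is that d=0.44 contradicts section 4.1, which reports that "The default group chose healthier foods than education controls, with no effect of incentives". That sentence is about healthfulness, while section 19.2 derives its d from calories, and an observed 0.44 can be non-significant in a small study. Deciding this would need the cited study.

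**Conclusion.** The concern holds. The stated 15 and 54 are not the sizes for pairwise differences of 0.96 and 0.44 at 80% power; those are 57 and 249 in three equal arms. At 54 in total, power for d=0.44 is about 25%, and at the full 100 without losses about 42%. These figures assume equal arms, a two-sided test, no baseline adjustment and no multiplicity correction. Baseline adjustment would raise them by an amount that depends on an unstated correlation.

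A reader might conclude that the trial is underpowered throughout, or the reverse, that it is adequately powered for Defaults against Control and needs nothing more. Neither is supported. Power for d=0.96 is about 80% at 18 per arm, but the number that will be randomised and retained is not given, and hypothesis 1a also involves Defaults against Online.

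**What to change.** Rewrite section 19.2 for the pairwise post-test contrast:
- State the test, its sidedness, the number per arm and any effect-size conversion.
- Replace 15 with 19 per arm (57 in three arms) and 54 with 83 per arm (249), and remove the claim that 54 gives 80% power for d=0.44.
- Give the number expected to be randomised and the difference detectable at that number: about d=0.96 at 18 per arm, 0.70 at 33 per arm. If baseline adjustment is to be relied on, state the assumed correlation and show a range.
- Say that contrasts involving Online are not powered for effects near d=0.44 and will be reported as estimates with confidence intervals.

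The cost is protocol wording and a less favourable stated power. The correction does not itself require more participants; whether the ceiling of 100 is enough cannot be judged until the expected losses are stated.
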